#### 11.2.1 Analysis of Primary (Safety) Endpoint Data

- Vital sign parameters outside the normal range will be listed and flagged for review.
- Orthostatic vital signs parameters for blood pressure outside the ranges specified in [Section 7.10](#) below will be listed and flagged for review.
- Descriptive statistics of absolute and change from Baseline (pre-dose) SBP, DBP, pulse rate, respiratory rate, and oral temperature at each timepoint, will be tabulated. The mean change from Baseline data will also be plotted across time.
- Twelve-lead ECG parameters will be listed with any values outside the normal range flagged. Descriptive statistics of absolute and change from Baseline (pre-dose) heart rate, PR, QRS, QT, and QTcF intervals at each timepoint, will be tabulated. The mean change from Baseline data will also be plotted across time.
- In addition, frequencies of QTcF data will be calculated according to the following categories:

For absolute values

- QTcF >450 msec (males) and >470 msec (females)
- QTcF >480 msec
- QTcF >500 msec

For change from Baseline

- QTcF increase >30 msec
- QTcF increase >60 msec

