## 4. Statistical Analysis and Reporting

### 4.1. Introduction

Data processing, tabulation of descriptive statistics, calculation of inferential statistics, and graphical representations will be performed primarily using SAS (release 9.4 or higher).

Commercially Confidential Information If the use of other software is warranted, the final statistical methodology report will detail what software was used for what purposes.

Continuous (quantitative) variable summaries will include the number of subjects (n) with non-missing values, mean, standard deviation (SD), median, minimum, and maximum.

Categorical (qualitative) variable summaries will include the frequency and percentage of subjects who are in the particular category for each possible value. In general, the denominator for the percentage calculation will be based upon the total number of subjects in the study population, unless otherwise specified. The denominator for by-visit displays will be the number of subjects in the relevant study population with non-missing data at each visit. If there is any missing value for a categorical analysis, a “Missing” category will be displayed as the last category in the table for the variable.

For weight, height, CCI one decimal place will be used for all summary statistics. For all other summaries, the minimum and maximum will be reported with the same degree of precision (i.e., the same number of decimal places) as the observed data. Measures of location (mean and median) and confidence interval boundaries will be reported to 1 degree of precision more than the observed data, up to 3 decimal places. Measures of spread (SD) will be reported to 2 degrees of precision more than the observed data, up to 3 decimal places.

Percentages will be presented to 1 decimal place, unless otherwise specified. Percentages equaling 0 or 100 will be displayed with no decimal places or percentage symbols.

Fractional numeric values will be presented with a zero to the left of the decimal point (for example, 0.12 – 0.30).

Unless otherwise indicated, all statistical tests will be conducted at the 0.05 significance level using 2-tailed tests, and *P* values will be reported. Corresponding 95% confidence intervals (CIs) will be presented for statistical tests, where applicable.

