#### **9.4.      Electrocardiograms**

12-lead ECGs will be obtained at Screening, Pre-dose, Day 1, Day 7, Day 14, and Day 21.

Descriptive summaries will be presented for ECG measures of PR interval, RR interval, mean heart rate, QRS interval, QT interval, and QTcF interval. Corrected QTc intervals will be calculated using Fridericia's correction formula. These summaries will be presented by study visit for the Safety Population overall and by cohort. The mean change from baseline (pre-dose) for each parameter will be plotted by study visit. Values outside the normal range will be flagged in the listings.

The number and percentage of subjects with normal, abnormal but not clinically significant, and abnormal and clinically significant ECG results will be summarized for the Safety population by study visit.

Additionally, QTcF data will be summarized by the following categories by study visit:

- QTcF > 450 msec to  $\leq$  480 msec
- QTcF > 480 msec
- QTcF > 500 msec
- Change from baseline > 30 msec to  $\leq$  60 msec
- Change from baseline > 60 msec

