**Same shell as Table 14.3.5.1.1**

**Programming Note:** Visits include Screening, Baseline, Day 1, Day 7 Pre-Dose, Day 7 Post-Dose, Day 14 Pre-Dose, Day 14 Post-Dose, and Day 21; parameters include PR interval (msec), RR interval (msec), mean heart rate (beats/min) QRS interval (msec), QT interval (msec), and QTcF interval (msec); SOURCE: Listing 16.2.8.4.2

Table 14.3.6.2.2  
Summary of 12-Lead Electrocardiogram Interpretation by Study Visit  
Safety Population

Study Visit Category	Cohort-1 (N=XX) n (%)	Cohort-2 (N=XX) n (%)	Overall (N=XX) n (%)
Screening			
Normal	XX (XX.X%)	XX (XX.X%)	XX (XX.X%)
Abnormal, Not Clinically Significant	XX (XX.X%)	XX (XX.X%)	XX (XX.X%)
Abnormal, Clinically Significant	XX (XX.X%)	XX (XX.X%)	XX (XX.X%)
Baseline [1]			
Normal	XX (XX.X%)	XX (XX.X%)	XX (XX.X%)
Abnormal, Not Clinically Significant	XX (XX.X%)	XX (XX.X%)	XX (XX.X%)
Abnormal, Clinically Significant	XX (XX.X%)	XX (XX.X%)	XX (XX.X%)
Day 1			
Normal	XX (XX.X%)	XX (XX.X%)	XX (XX.X%)
Abnormal, Not Clinically Significant	XX (XX.X%)	XX (XX.X%)	XX (XX.X%)
Abnormal, Clinically Significant	XX (XX.X%)	XX (XX.X%)	XX (XX.X%)

Note: Percentages are n/Number of subjects in the Safety Population and respective Protocol Amendment\*100.

[1] The baseline value for each variable is the last observation recorded prior to the first dose of treatment.

SOURCE: Listing 16.2.8.4.1

**Programming note:** Continue for Day 7 Pre-Dose, Day 7 Post-Dose, Day 14 Pre-Dose, Day 14 Post-Dose, and Day 21.

Table 14.3.6.2.3  
Summary of QTcF Values by Study Visit  
Safety Population

Study Visit Category	Cohort-1 (N=XX) n (%)	Cohort-2 (N=XX) n (%)	Overall (N=XX) n (%)
Screening			
QTcF Value			
> 450 msec to ≤ 480 msec [1]	XX (XX.X%)	XX (XX.X%)	XX (XX.X%)
> 480 msec	XX (XX.X%)	XX (XX.X%)	XX (XX.X%)
> 500 msec	XX (XX.X%)	XX (XX.X%)	XX (XX.X%)
Baseline [3]			
QTcF Value			
> 450 msec to ≤ 480 msec [1]	XX (XX.X%)	XX (XX.X%)	XX (XX.X%)
> 480 msec	XX (XX.X%)	XX (XX.X%)	XX (XX.X%)
> 500 msec	XX (XX.X%)	XX (XX.X%)	XX (XX.X%)
Day 1			
QTcF Value			
> 450 msec to ≤ 480 msec [1]	XX (XX.X%)	XX (XX.X%)	XX (XX.X%)
> 480 msec	XX (XX.X%)	XX (XX.X%)	XX (XX.X%)
> 500 msec	XX (XX.X%)	XX (XX.X%)	XX (XX.X%)
QTcF Increase from Baseline [3]			
> 30 msec to ≤60 msec	XX (XX.X%)	XX (XX.X%)	XX (XX.X%)
> 60 msec	XX (XX.X%)	XX (XX.X%)	XX (XX.X%)

Note: Percentages are n/Number of subjects in the Safety Population and respective Protocol Amendment\*100.

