[1] Percentages are based on the number of male subjects in the Safety Population.

[2] Percentages are based on the number of female subjects in the Safety Population.

[3] The baseline value for each variable is the last observation recorded prior to the first dose of treatment

SOURCE: Listing 16.2.8.4.2

**Programming note:** Continue for Day 7 Pre-Dose, Day 7 Post-Dose, Day 14 Pre-Dose, Day 14 Post-Dose, and Day 21.

Table 14.3.6.4  
Summary of Columbia-Suicide Severity Rating Scale (C-SSRS)  
Safety Population

C-SSRS Section C-SSRS Item	Cohort-1 (N=XX)		Cohort-2 (N=XX)		Overall (N=XX)	
	Pre-treatment (N=XX)	Post-treatment (N=XX)	Pre-treatment (N=XX)	Post-treatment (N=XX)	Pre-treatment (N=XX)	Post-treatment (N=XX)
Suicidal Ideation	XX (XX.X%)	XX (XX.X%)	XX (XX.X%)	XX (XX.X%)	XX (XX.X%)	XX (XX.X%)
Wish to be Dead	XX (XX.X%)	XX (XX.X%)	XX (XX.X%)	XX (XX.X%)	XX (XX.X%)	XX (XX.X%)
Non-Specific Active Suicidal Thoughts	XX (XX.X%)	XX (XX.X%)	XX (XX.X%)	XX (XX.X%)	XX (XX.X%)	XX (XX.X%)
Active Suicidal Ideation with Any Methods	XX (XX.X%)	XX (XX.X%)	XX (XX.X%)	XX (XX.X%)	XX (XX.X%)	XX (XX.X%)
Active Suicidal Ideation with Some Intent	XX (XX.X%)	XX (XX.X%)	XX (XX.X%)	XX (XX.X%)	XX (XX.X%)	XX (XX.X%)
Active Suicidal Ideation with Specific Plan	XX (XX.X%)	XX (XX.X%)	XX (XX.X%)	XX (XX.X%)	XX (XX.X%)	XX (XX.X%)
Suicidal Behavior	XX (XX.X%)	XX (XX.X%)	XX (XX.X%)	XX (XX.X%)	XX (XX.X%)	XX (XX.X%)
Actual Attempt	XX (XX.X%)	XX (XX.X%)	XX (XX.X%)	XX (XX.X%)	XX (XX.X%)	XX (XX.X%)
Subject Engaged in Non-Suicidal Self-Injurious Behavior	XX (XX.X%)	XX (XX.X%)	XX (XX.X%)	XX (XX.X%)	XX (XX.X%)	XX (XX.X%)
Interrupted Attempt	XX (XX.X%)	XX (XX.X%)	XX (XX.X%)	XX (XX.X%)	XX (XX.X%)	XX (XX.X%)
Aborted Attempt	XX (XX.X%)	XX (XX.X%)	XX (XX.X%)	XX (XX.X%)	XX (XX.X%)	XX (XX.X%)
Preparatory Acts or Behavior	XX (XX.X%)	XX (XX.X%)	XX (XX.X%)	XX (XX.X%)	XX (XX.X%)	XX (XX.X%)
Suicidal Behavior	XX (XX.X%)	XX (XX.X%)	XX (XX.X%)	XX (XX.X%)	XX (XX.X%)	XX (XX.X%)

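### QTcF Table 14.3.6.2.3 gives a row that names no sex a male-only denominator, and the protocol's sex-specific QTcF count is in no visible planned table

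*SAP*

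**What the plan says.** **Protocol 11.2.1** (repeated in the synopsis) puts the QTcF frequencies under its primary safety analysis: "In addition, frequencies of QTcF data will be calculated according to the following categories". The first category is "QTcF >450 msec (males) and >470 msec (females", with no upper bound. The others are above 480 msec, above 500 msec, and increases above 30 and above 60 msec.

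**SAP 9.4** has its own list: "Additionally, QTcF data will be summarized by the following categories by study visit". The categories are above 450 to 480, above 480, above 500, change above 30 to 60, and change above 60 msec. None is split by sex and none uses 470 msec.

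**SAP 14.2, shell of Table 14.3.6.2.3.** At Screening, Baseline and Day 1 the row reads "> 450 msec to ≤ 480 msec [1", the last characters being the marker for footnote 1. The programming note extends the layout to the remaining visits. The notes under the table are:
- General Note: "Percentages are n/Number of subjects in the Safety Population and respective Protocol Amendment".
- Footnote 1: "Percentages are based on the number of male subjects in the Safety Population".
- Footnote 2: "Percentages are based on the number of female subjects in the Safety Population". No row carries this marker.

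**SAP section 10.** The visible text on changes from the protocol mentions TETRAS ratings and nothing about QTcF. Part of the section is redacted.

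**The concern.** A percentage can be read only if numerator and denominator describe the same people. Here the row label and SAP 9.4 point to everyone, while the footnote points to men. A programmer following the shell has to guess whether to count women, and the two guesses give different numbers under the same label.

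The unused female footnote would fit a female row that was removed when the category changed; that is an inference, not something the SAP says. It leads to the second issue. The protocol planned a count against separate male and female limits, and the table built to report QTcF categories no longer gives it. At stake is whether a reader can see how many men and how many women crossed the limits that the protocol set for each.

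**Working it through.** The plan gives no figure to reproduce here. The check sets the texts side by side and uses simple proportions.

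**Inputs.** Up to 30 subjects (SAP 3.2). The number of each sex is not given, so I assume 10 to 20 men of 30. The QTcF values below are illustrative.

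**Step 1: denominator.** If both sexes are counted over men, inflation = (n/men) ÷ (n/30) = 30/men, which is one over the male share. With one man and one woman in the band:

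| Men of 30 | Inflation 30/men | Both sexes over men | Both sexes over all | Men only over men |
|---|---|---|---|---|
| 10 | 3.00 | 2/10 = 20.0% | 2/30 = 6.7% | 1/10 = 10.0% |
| 12 | 2.50 | 2/12 = 16.7% | 6.7% | 1/12 = 8.3% |
| 15 | 2.00 | 2/15 = 13.3% | 6.7% | 1/15 = 6.7% |
| 18 | 1.67 | 2/18 = 11.1% | 6.7% | 1/18 = 5.6% |
| 20 | 1.50 | 2/20 = 10.0% | 6.7% | 1/20 = 5.0% |

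The last column is a valid male rate, but the row is not labelled as one and the woman is left out of it.

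**Step 2: the Screening row.** Exclusion criterion 15 in protocol 4.2 bars men above 450 msec and women above 470 msec at Screening. Apart from deviations, or differences between site and central readings, anyone in the Screening band is therefore a woman above 450 and up to 470 msec. Footnote 1 would express her as a percentage of men. If only men are counted, the row is empty by design.

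**Step 3: can the protocol's count be rebuilt?** Take 15 men and 15 women, with men at 455 and 485 msec, women at 460 and 475 msec, and everyone else at or below 450.
- Protocol: men above 450 = 2/15 = 13.3%; women above 470 = 1/15 = 6.7%; 3 subjects in all.
- SAP band, both sexes: 455, 460 and 475, so 3 subjects. This is 3/15 = 20.0% under footnote 1 or 3/30 = 10.0% over all subjects.
- SAP band, men only: 455, so 1/15 = 6.7%.
- SAP above 480: 485, so 1/30 = 3.3%.

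With both sexes counted, the two SAP rows give 3 + 1 = 4 subjects above 450 msec. The extra subject is the woman at 460, who is within the female limit. With men only, neither woman appears. In neither case do the printed rows return 2 men and 1 woman.

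**Step 4: contrast with the change categories.** The SAP rows for above 30 to 60 and above 60 msec add up to the protocol's above-30 category, so that re-cut loses nothing. The absolute category is different because it drops a cut point and a split.

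**Step 5: other sources.** Listing 16.2.8.4.2 holds individual QTcF values but its shell has no sex column. Sex is in Listing 16.2.4.1. The count can be made only by merging the two.

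**The case against.** **The percentage may be correct.** A reader might infer that the printed figure is certainly inflated. The documents do not support that. Inflation needs women in the numerator, and the shell is silent. If only men are counted, the figure is a true male rate. The supportable statement is that the row is either inflated or leaves women out.

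**A row footnote may override a general Note.** Table 14.1.2.1 does this: an all-subject Note, with a female-only footnote for child-bearing potential. This stands, so the difference from the Note is not itself the defect. In Table 14.1.2.1, however, the question applies only to women. Here the row has no sex label and the companion footnote has no row.

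**SAP 4.1 adds a third rule**, for subjects with data: "The denominator for by-visit displays will be the number of subjects in the relevant study population with non-missing data at each visit". A reader might count this as a further fault of the QTcF table. The mismatch between that rule and the Note recurs in other by-visit tables. It should be settled for the whole plan, and changing this table alone would set it apart from the others.

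**The SAP may refine the protocol.** Protocol 11.2 calls its text a summary and leaves detail to the SAP. With both sexes counted, the band plus the above-480 row captures everyone above 450 msec. Out-of-range values are also flagged in the listings. This lowers the stakes but does not supply the protocol's sex-specific count.

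**Conclusion.** The point holds on two counts. First, the row's label and its footnote do not match, so its percentage is either 1/(male share) too high (1.5 to 3 times for an assumed 20 to 10 men of 30) or leaves out women in the band. Second, the protocol's count by sex-specific limit is in no visible planned table.

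The impact is limited. The table is descriptive, the primary endpoint (treatment-emergent adverse events) is unaffected, the counts are printed, the footnote does not touch the above-480, above-500 or change rows, and individual values are listed.

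Three stronger readings are not supported:
- *Women above 470 msec go unseen.* If both sexes are counted, none is missed; what is lost is the split. If only men are counted, women above 470 and up to 480 msec are missing from the table but remain in the listing.
- *The change was left undeclared.* Only the visible part of SAP section 10 can be read, so a declaration in the redacted part cannot be ruled out.
- *The table also wrongly collapses serial post-dose ECGs.* The protocol's call for results at each time point attaches to the descriptive statistics, not to the QTcF frequencies. A rule for reducing repeated readings may sit in redacted parts of SAP 6.1. The ECG schedule under Amendment 1, which governed Cohort-1, is not in the documents, and protocol 7.8 gives two different lists of times for Days 7 and 14.

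**What to change.** **Preferred.** In both SAP 9.4 and the shell, replace the band with two rows: males above 450 msec, carrying footnote 1, and females above 470 msec, carrying footnote 2. Keep the above-480, above-500 and change rows on all subjects. SAP 9.4 must be amended as well as the shell, or text and table will disagree.

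**Alternative.** Keep the band for all subjects, delete footnotes 1 and 2, and record the departure from protocol 11.2.1 in SAP section 10. This makes the percentage readable but still does not give the protocol's sex-specific count.

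**Cost.** The preferred fix adds one row per visit. The shell shows three visits and its programming note adds five, so 3 + 5 = 8 rows, plus the text edits. The alternative adds no rows. Neither needs new data.

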##### **9.5.3.    Columbia Suicide Severity Rating Scale**

The C-SSRS is a questionnaire that prospectively assesses Suicidal Ideation and Suicidal Behavior. At the Pre-dose visit, the "baseline" version of the C-SSRS will be administered. This version assesses Suicidal Ideation and Suicidal Behavior during the subject's lifetime and during the past 12 months. At the Day 14 and Day 21 visits (and the Early Termination visit for subjects withdrawing early), the "since last visit" version will be administered.

Suicidality data collected on the C-SSRS will be listed for all subjects in the Safety Population. Tables will include results from the Suicidal Ideation and Suicidal Behavior sections of the C-SSRS. Frequencies and percentages of subjects with a response of "Yes" at any point on the

Suicidal Ideation and Suicidal Behavior items will be summarized for the Safety Population (overall and by cohort).

Commercially Confidential Information

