Note: Percentages are n/Number of subjects in the Safety Population and respective Protocol Amendment\*100. The C-SSRS scale consists of a Baseline evaluation that assesses the lifetime and more recent experience (past 12 months) of the subject with suicidal ideation and behavior, a baseline evaluation that focuses on suicidality since Screening that occurs before first dose of study drug (all of which is summarized under "pre-treatment"), and a post-baseline evaluation ("post-treatment") administered at either Day 21 visit or early termination visit for discontinued subjects, which focuses on suicidality since the last study visit. Subjects are counted once for each C-SSRS section and once for each C-SSRS item answered "Yes" in pre-treatment and post-treatment.

SOURCE: Listing 16.2.8.6

Commercially Confidential Information

Commercially Confidential Information

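### The C-SSRS summary table pools lifetime, 12-month and since-Screening answers in one pre-treatment column with no within-subject row, so it does not reliably identify new or worsened suicidality, and it leaves open whether non-suicidal self-injury enters the behavior total

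*SAP*

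**What the plan says.** SAP 9.5.3 plans frequencies and percentages of subjects with a Yes on the ideation and behavior items, for the Safety Population, overall and by cohort. The display is Table 14.3.6.4, which has one pre-treatment and one post-treatment column per cohort.

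The note to that table defines the columns:

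- **Pre-treatment.** A baseline evaluation that "assesses the lifetime and more recent experience (past 12 months) of the subject with suicidal ideation and behavior", together with "a baseline evaluation that focuses on suicidality since Screening that occurs before first dose of study drug". The note says that all of this goes under pre-treatment.
- **Post-treatment.** An evaluation "administered at either Day 21 visit or early termination visit for discontinued subjects, which focuses on suicidality since the last study visit".
- **Counting.** "Subjects are counted once for each C-SSRS section and once for each C-SSRS item answered" Yes, in each of the two columns.

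Among the rows under Suicidal Behavior, between Actual Attempt and Interrupted Attempt, is "Subject Engaged in Non-Suicidal Self-Injurious Behavior". The label Suicidal Behavior appears twice, at the head of the block and as its last row. The shell has no shift, new-onset or worsening row.

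Listing 16.2.8.6 shows each subject's visit, date, reference period, item and result.

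**The concern.** The two columns answer different questions. One asks whether the subject has ever reported ideation or behavior. The other asks whether the subject has done so in the last few weeks. Set side by side as percentages, they invite a before-and-after reading that the look-back periods do not support, and the difference in length favors the drug. Because the counts are marginal, the table also does not say whether a post-treatment Yes comes from someone with prior history or from someone new.

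This departs from the SAP's handling of other safety data. Treatment-emergent adverse events require onset or worsening after first dose (SAP 6.1.8 and 9.1). Laboratory values, vital signs and orthostatic signs have shift tables (SAP 13.3), and QTcF has increase-from-baseline rows (Table 14.3.6.2.3). SAP section 9 names the C-SSRS as a safety measure in a study whose primary objective is safety, yet its visible summary table has no such comparison.

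The self-injury row raises a separate question of definition. If it feeds the section count, a subject with no suicidal behavior is reported as having some.

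**Working it through.** The plan gives no figure for the C-SSRS, so there is nothing to reproduce. I take N = 30 (protocol 11.2.4: approximately 30; SAP 3.2: up to 30).

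**1. Length of the look-backs**

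Inputs: Day 1 may fall up to 3 business days after the Baseline visit (protocol 6.1.3), which I take as 0 to 5 calendar days to allow for a weekend. The Day 21 window is Day 20 to 22 and the Day 14 window is Day 13 to 15 (SAP Table 2). Age is 18 to 75.

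- Baseline C-SSRS to Day 21: from 20 − 1 + 0 = 19 days to 22 − 1 + 5 = 26 days.
- If the last study visit is literally Day 14: from 20 − 15 = 5 days to 22 − 13 = 9 days.
- 12 months against that window: 365/26 = 14.0 to 365/19 = 19.2 times as long; 365/21 = 17.4 at 21 days.
- Lifetime against 21 days: 18 × 365.25/21 = 313 to 75 × 365.25/21 = 1,304 times as long.

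**2. What unequal windows do to the display**

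Assume a constant annual rate r of a first Yes. The documents give no rate, so I use 2%, 5% and 10%. Expected subjects with a Yes are 30 × (1 − e^(−r)) over 12 months and 30 × (1 − e^(−r × m × 21/365)) over 21 days, where m multiplies the rate on drug.

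| r | 12 months | 21 days, m = 1 | 21 days, m = 5 |
|---|---|---|---|
| 2% | 0.59 | 0.03 | 0.17 |
| 5% | 1.46 | 0.09 | 0.43 |
| 10% | 2.85 | 0.17 | 0.85 |

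Even a five-fold rise on drug leaves the expected post-treatment count below the 12-month count. Lifetime answers widen the gap.

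**3. What can be read about new cases**

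With a subjects Yes before and b Yes after, the number of new cases lies between max(0, b − a) and min(b, 30 − a).

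| Pre-treatment | Post-treatment | Possible new cases |
|---|---|---|
| 0 | 1 | exactly 1 |
| 1 | 1 | 0 to 1 |
| 1 | 3 | 2 to 3 |
| 4 | 2 | 0 to 2 |
| 5 | 2 | 0 to 2 |

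The fourth row would print as 13.3% falling to 6.7%. The same figures fit two recurrences of old history and two wholly new cases.

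**4. Non-suicidal self-injury**

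The item sits within the Suicidal Behavior block. The note counts a subject once per section, and neither the note nor SAP 9.5.3 excludes the item. If it is counted, one subject with only this item adds 1/30 = 3.3 percentage points to the total.

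**5. Passages that do not agree**

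- The table note relies on an evaluation since Screening. The schedules (protocol Appendix A Table 2, SAP Table 1) place the first C-SSRS at Baseline and show none at Screening. Protocol 7.12 describes the baseline version as covering lifetime and a predefined period.
- SAP 9.5.3 has a since-last-visit C-SSRS at both Day 14 and Day 21. Footnote 25 of both schedules says Day 14 is not needed unless it is an Early Termination visit, and the table note draws only on Day 21 or early termination. If Day 14 assessments are done, Day 21 covers only 5 to 9 days, and the note gives the Day 14 answers no column.

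**The case against.** The best defense is that this is a descriptive table in a study of about 30 subjects. No C-SSRS test, change score or claim of improvement is planned. Every subject's answers are listed by reference period, so a medical reader can find new or worse cases directly. Clinically relevant events should also appear as adverse events. Text is redacted around the C-SSRS passages, so one cannot say that no other summary exists. All of this stands and limits the consequence. It does not repair the table: a listing does not correct a summary that mixes unequal periods and has no treatment-emergent count.

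Three stronger readings are tempting, and the documents do not support them:

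- **That the table cannot show new suicidality.** It counts every post-treatment Yes, and a row with none before and one or more after is new, because the pre-treatment column includes lifetime history.
- **That it will nearly always show a fall.** This depends on an unknown baseline rate. If lifetime ideation were 5%, the chance that none of 30 subjects has any would be 0.95^30 = 21%. Exclusion 25 removes uncontrolled major psychiatric disorder, and other exclusions are redacted.
- **That self-injury is counted as suicidal behavior.** This is the natural reading of the row's position and the counting rule, but no sentence says so. The item has its own row, and the duplicated label leaves the total undefined.

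A further fair point is that a 12-month column is still much longer than three weeks. Splitting the column alone would not remove the mismatch. The within-subject rows are what answer the question.

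**Conclusion.** The point holds as a defect of presentation and definition in one safety table. The pooling is explicit in the note, the absence of a within-subject row is plain from the shell, and the bounds on new cases follow from arithmetic without any assumed rate. The direction of the lean rests on the window lengths: about three weeks if the reference is the Baseline C-SSRS, 5 to 9 days if it is the Day 14 visit, against at least 12 months. The expected counts in the illustration rest on assumed rates and show direction only.

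The self-injury issue is an ambiguity worth up to 3.3 percentage points per affected subject at N = 30, not a demonstrated miscount.

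The primary endpoint, the efficacy analyses and study conduct are unaffected. The change is still worth making, because a reader of the study report will see the table before the listing.

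**What to change.** 1. In Table 14.3.6.4, split Pre-treatment into Lifetime and Past 12 months. Drop the since-Screening period from the note unless a scheduled C-SSRS supports it.
2. Add rows for treatment-emergent ideation and treatment-emergent behavior: a post-treatment Yes in a subject with No, or a lower ideation category, in the past 12 months. State that this is a within-subject comparison.
3. State that non-suicidal self-injury is shown in its own row and does not enter the Suicidal Behavior total. Rename or remove the duplicate Suicidal Behavior row so that the total has one definition.
4. Reconcile the Day 14 C-SSRS in SAP 9.5.3 with footnote 25 and the table note, and say which assessments feed the post-treatment column and over what period.

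The cost is one table shell, its note, a few lines in SAP 9.5.3 and some extra programming. Items 1 to 3 need no new data, because Listing 16.2.8.6 already holds the answers by subject and reference period. One limit remains: a subject with ideation earlier in the past 12 months and the same level on drug will not count as emergent, so the listing should still be read alongside.
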